Attachment UUU

Title: *Development of a multiple health behavior change intervention for cardiovascular risk reduction among people experiencing homelessness: The CV-HOMES study (Aim 2)*

Drug or Device Name(s): Not applicable (N/A)

NCT NCT06025721

Sponsor: The C2DREAM Study (P50MD017342) via the National Institute for Minority Health and Health Disparities (NIMHD).

Protocol Date: 03/19/2024

Revision Date(s):

Study Principal Investigator:

[name] [name], MSc
[name]
[name]
[contact]
email: [contact]

Other Investigators:

[name]

Protocol Synopsis

Study Title	Development of a multiple health behavior change intervention for cardiovascular risk reduction among people experiencing homelessness: The CV-HOMES study (Aim 2)
Funder	National Institute on Minority and Health Disparities (P50MD017342): C2Dream pilot grant
Clinical Phase	N/A
Study Rationale	People experiencing homelessness die on average 10 years earlier than their housed peers due to poorly controlled chronic physical and behavioral health conditions. Cardiovascular (CV) disease is a leading cause of death among people experiencing homelessness resulting from modifiable health behaviors. High risk behaviors are more common among people experiencing homelessness with high rates of smoking (e.g., 73-79%) and low rates of fruit/vegetable intake (e.g., 64% <5 servings/day) and inadequate physical activity (e.g., 46% do not meet recommended guidelines). Access and insurance barriers compound individual challenges leading to even lower rates of medication adherence than general U.S. population.
Study Objective(s)	
Primary
 
 • Assess the feasibility and acceptability of CV-HOMES, a behavioral activation based coaching program targeting multiple health behaviors, for people who have experienced homelessness in a single arm treatment development trial (n=8). • Assess the feasibility of measuring cardiovascular risk in this population at 2 time points.
Test Article(s)	One-on-one behavioral activation based coaching intervention to support behaviors to improve cardiovascular health
Study Design	Single arm treatment-development and feasibility trial
Participant Population	Patient inclusion criteria are:
Key Criteria for Inclusion and Exclusion:	(1) Moderate to high CV risk defined as self-reported diagnoses by a medical professional of high blood pressure, high cholesterol, prediabetes, type 2 diabetes, or heart disease. (2) Experience of homelessness per the HEARTH Act which includes living in a supported housing facility (2011). (3) English-speaking, (4) and willingness to engage in coaching about changes to ≥1 health behavior related to cardiac risk that align with patients' personal CV risk behaviors. Medical diagnoses and medications will be confirmed in medical records after enrollment.
	Patient exclusion criteria will include conditions raising risk for coercion or limitation of capacity to ethically consent to research: (1) active intoxication, (2) active psychosis or dementia, (3) active legal commitment (per search of publicly available civil court records) or (4) pregnancy or lactation. This is aligned with previous studies by this team (K23DK118117).
	We will further confirm capacity to consent using a brief quiz (see attachments).
Number Of Participants	Total Number of Participants: 8

	
Total Number at Hennepin Healthcare: 8
 
Total Number of Sites: 1

Study Duration	
Each participant will be enrolled for 16 weeks.
 
The entire study is expected to last one year.

Study Phases	(1) Screening : screening for eligibility and obtaining consent, baseline assessment
Screening	(2) Intervention : study intervention with counselor support approximately weekly in-person and/or by phone x 12 weeks
Intervention	
Follow-Up	(3) Follow-up : final assessment
Efficacy Evaluations	
 • Cardiovascular health as measured by the American Heart Association's Life's Essential 8 score.¹⁸ This includes: 
 ○ Self-reported cardiovascular health behaviors (eating better, being more active, taking medications as prescribed, quitting tobacco, getting healthy sleep) ○ Blood pressure and body mass index (height, weight) ○ Cholesterol and Hemoglobin A1c measured by point-of-care fingerstick or venous blood draw ○ Skin carotenoid measurement by VEGGIE METER • Self-reported medication adherence • Self-reported psychological wellness • Self-reported drug and alcohol use • Self-reported health care use
Safety Evaluations	Not applicable in this single arm trial
Statistical And Analytic Plan	
The primary endpoint of this study is the feasibility and acceptability of the program to participants in this treatment development phase. We will summarize themes in the end-of treatment interview, assess satisfaction via structured survey, and assess treatment dose received via frequency, length, and type of communications with study staff.
 
We will conduct exploratory analyses on our eventual primary behavioral endpoint of cardiovascular health. We will refine our use of patient-reported outcomes for use in a future randomized pilot trial.

Data And Safety Monitoring Plan	
[name] (PI) will work closely with study staff to monitor the quality of data collected at assessment. This treatment development study (N=8), does not meet NIH criteria requiring a Data Safety Monitoring Board (DSMB), however [name] will oversee a detailed safety monitoring plan.

TABLE 1: SCHEDULE OF STUDY PROCEDURES

Study Phase	Eligibility screening	Consent, Baseline assessment	Treatment sessions										Follow-up visit
			1	2	3	4	5	6	7	8	9	10	
Visit Number			1	2	3	4	5	6	7	8	9	10	
Study Weeks	0	1	2-3	4	5	6	7	8	9	10	11	12	13-16
Confirm communication preferences	X	X	X				X						X
Review Inclusion/Exclusion Criteria	X	X											
Informed Consent		X											
Demographics/Medical History, experiences of discrimination		X											
Vital Signs: BP, HR		X											X
Height and Weight		X											X
Point of care LDL and blood glucose		X											X
Skin Carotenoids		X											X
Medication review		X											X
Self-report survey measures		X											X
Satisfaction with intervention													X

1.1 Introduction

The overall goal of this project is to expand our team's existing evidence-informed programs to specifically target multiple health behavior change to decrease the cardiovascular (CV) health risk of people experiencing homelessness in Minnesota and beyond. This is relevant to health disparities given the disproportionate number of Black, Indigenous, and other people of color (BIPOC) who are homeless. We plan a sequential exploratory mixed methods study design for treatment development familiar to our team from prior work (K23DK118117) with ongoing input from our community-engaged research team (Fig 2).

Aim 2. Assess the feasibility and acceptability of CV-HOMES for people who have experienced homelessness in a single arm treatment development trial (n=8). We hypothesize feasibility (e.g., recruitment, treatment engagement, retention) and acceptability (of study procedures and CV-HOMES treatment). This will include examining changes in the American Heart Association's Life's Essential 8 score as our targeted clinical outcome.

1.2 Relevant Literature and Data

People experiencing homelessness are disproportionately Black, Indigenous, and other people of color. For example, in Minnesota in 2018 an estimated 37% of adults experiencing homelessness identified as African American (compared to 6% of Minnesota adults) and 12% identified as American Indian (compared to 1% of Minnesota adults).¹ This results directly from structural racism in the form of discrimination in housing,² education, and employment leading to a substantial wealth gap between BIPOC and white Minnesotans.

People experiencing homelessness die on average 10 years earlier than their housed peers due to poorly controlled chronic physical and behavioral health conditions. Barriers to optimal health exist at multiple levels and throughout the life course of people experiencing homelessness.³ In previous work we demonstrated disproportionately high rates of CV health conditions among Minnesotans who were homeless (e.g., in 2018 27% reported hypertension, and 11% heart disease). We also found high rates of behavioral health conditions (e.g., in 2018 57% reported a mental health diagnosis and 42% substance use). There CV conditions and behavioral health comorbidities overlap significantly.⁴

CV disease is a leading cause of death among people experiencing homelessness resulting from modifiable health behaviors. High risk behaviors are more common among people experiencing homelessness with high rates of smoking (e.g., 73-79%)⁵ and low rates of fruit/vegetable intake (e.g., 64% <5 servings/day) and inadequate physical activity (e.g., 46% do not meet recommended guidelines).⁶ Access and insurance barriers compound individual challenges leading to even lower rates of medication adherence than general U.S. population.

Current permanent supportive housing (Housing First) models offer substantial opportunity to reduce homelessness but fail to achieve health improvements. Minnesota's 2022-2023 Affordable Housing Plan commits more than \$3 billion to affordable housing solutions aimed at ending homelessness.⁷ The National Academy of Medicine concluded "no substantial published evidence as yet to demonstrate that PSH improves health outcomes or reduces health care costs."⁸ A large trial in Canada specifically demonstrated that Housing First models of general support did not lead to sustained CV risk reduction over usual care,⁹ suggesting that housing is necessary but not sufficient to change CV risk. This demonstrates a critical need to establish health behavior change models to reduce CV risk that are adjunctive to housing support.

Wellness coaching tailored to the overlapping physical, behavioral, and social needs of people experiencing homelessness offers promise to reduce health disparities.

1.3 Name and Description of Intervention

Intervention content. Behavioral activation (BA) is an empirically supported counseling treatment has its underpinnings in the behavioral model of depression. BA seeks to reconnect participants with sources of positive reinforcement via collaborative values-based goal-setting.¹² The core activity in BA is the careful setting of between session goals and a structured review of those goals in the following session. BA is distinct from many other empirically supported depression treatments in that providers without mental healthcare backgrounds can be trained to deliver BA with fidelity. BA has been successfully leveraged to simultaneously target health behavior engagement and mood amelioration in a variety of medical populations,^{13,14} including research by our team. For example, [name] is conducting an ongoing RCT of a BA based treatment targeting mood and smoking cessation post-cardiac event, [name] is leading an on ongoing randomized trial targeting medication adherence and psychological wellness in people with diabetes who are homeless, and both just published an open trial of multiple health behavior change in cardiac patients with depression. CV-HOMES will build off of these three existing manuals.¹⁰ **The CV-HOMES manual will target ≥ 1 health behaviors to reduce CV risk (quitting or reducing tobacco use, medication adherence, physical activity, healthy eating, or sleep), psychological wellness, and referrals to meet social and behavioral needs.**

Consistent with our prior work, CV-HOMES will be delivered via 8-10 sessions spanning 12 weeks. Sessions 1-2 (50 minutes each) will be completed in-person whenever possible and sessions 3-10 (30 minutes each) will be completed in-person or by phone or videoconference per participant preference. CV-HOMES will be delivered by a bachelor's level providers (e.g., social worker, health educator) or higher providers. We will use 1-2 of such providers already employed in our research labs ([name], [name]). [name] will participate in coaching the first few participants and train and supervise interventionists throughout the trial with support from [name] as needed. Interventionists will be referred to as a "wellness coaches" per Quorum team feedback from our previous work. We will also notify the patient's primary care provider and any other patient requested providers (e.g., cardiologist, psychiatrist) of their study involvement.

CV-HOMES goal setting structure: Between session goal setting will focus on pleasant/valued activities to improve mood and goals directly aimed at improving relevant health behaviors. The patient and coach will collaboratively agree on goals that are individualized for the patient's context. Goals are set in manageable increments (to increase self-efficacy through early success), and reviewed in detail to problem-solve any barriers encountered. All goals are explicitly written down (e.g., to-do list, daily planner) or otherwise scheduled (e.g., entered into cell phone calendar). As needed and with permission, study staff will send an automated email or text message between sessions to remind the patient to complete their goals.

Health behavior (i.e., quitting or reducing tobacco use, medication adherence, physical activity, healthy eating, or sleep) goals will be set alongside mood-focused goals using the process above, as has been successfully done in previous studies.¹³ If multiple health behaviors are relevant for a patient, they will be targeted sequentially. That is, coaching will initially focus on one behavior and if sufficient progress is made, the participant and coach will collaboratively decide if goals should be set targeting a second and/or third health behavior. We chose sequential targeting because simultaneous targeting of multiple health behaviors is cognitively demanding for the patient and

associated with increased drop-out.¹⁵ Tools will be provided to participants to support health behavior goals (see Session 2 below).

The content of goals will be integrated to maximize both mood improvement and health behavior change. For example, for a participant trying to quit smoking, goals will be set to avoid contact with smoking triggers.

Treatment Fidelity. Coaches will complete treatment fidelity checklists. All sessions will be audio recorded. [name] will monitor fidelity via review of all recordings and provide feedback to coaches during weekly supervision meetings. Audio recordings will be stored securely.

Baseline only measures. At baseline we will collect demographics to describe the sample. We will also collect the Discrimination in Medical Settings scale¹⁶ given the high degree of discrimination found in previous data with this population and congruent with the larger C2DREAM grant.

Primary outcomes of this proof-of-concept, single arm, treatment development pilot trial are feasibility (e.g., recruitment, treatment engagement, retention) and acceptability (of study procedures and CV-HOMES treatment via satisfaction survey and post-treatment interview). Secondary outcomes will include efficacy measures we plan to use in a future randomized pilot study and eventual R01 randomized trial. Outcomes will be collected during screening and at a baseline and post-treatment assessment visits. We will examine feasibility by tracking success of planned methods of recruitment. We will track the ratio of invitations to screenings and screenings to enrollments. We will also examine treatment engagement and retention via the number of attended assessment visits and coaching sessions. We will use the 8-item Client Satisfaction Questionnaire and a 20 minute qualitative post-treatment exit interview to track acceptability of activities as has worked well in several prior trials by our team.¹⁷

1.4 Selection of Treatment Dosages

Treatment doses are similar to a multiple health behavior change intervention currently underway by [name] (“Development of an Integrated Depression and Behavioral Risk Factor Reduction Intervention for Secondary Prevention following Acute Coronary Syndrome,” R03HL136540; “Multisite feasibility of BA-HD: An integrated depression and behavioral risk factor reduction coaching program following acute coronary syndrome,” R34HL165716), primary mentor on this study. This is also in line with the prior work of our team in diabetes with a similar population (D-HOMES, K23DK118117) which has been acceptable to participants. During this treatment development phase we will monitor and adjust the number and duration of planned sessions based on the data from participants if needed.

1.5 Relevant References *See references at end of document.*

1.6 Compliance Statement

This study will be conducted in full accordance of all applicable Hennepin Healthcare Research Policies and Procedures and all applicable Federal and State laws and regulations. All episodes of noncompliance will be documented and reported according to the Prompt Reporting Guidelines, Attachment EEE, of the Hennepin Healthcare IRB Policies and Procedures.

The investigators will perform the study in accordance with this protocol, will obtain informed consent and will report unanticipated problems involving risks to Participants or others and SAEs in accordance with The Hennepin Healthcare IRB Policies and Procedures and all Federal

requirements. Collection, recording, and reporting of data will be accurate and will ensure the privacy, health, and welfare of research Participants during and after the study.

2 STUDY OBJECTIVES

The purpose of the study is to develop and pilot test a multiple health behavior intervention using behavioral activation to improve cardiovascular health for people who have experienced homelessness with elevated cardiovascular risk.

2.1 Primary Objective (or Aim)

The primary objective of this study is to determine whether a 10-session behavioral activation support program is feasible and acceptable to people with cardiovascular risk who have experienced homelessness. The outcomes we will use to assess this treatment development phase of our work will be our ability to recruit and retain participants, the dose of treatment we can deliver (i.e., participant's attendance and follow-up with scheduled sessions and treatment activities), and participants' report of their satisfaction and overall experience during participation in a structured survey and qualitative interview.

2.2 Secondary Objectives (or Aim)

The secondary objectives will be to edit protocols and treatment manual instructions to optimally support participants. We will:

- Clarify recruitment and retention strategies for people with cardiovascular risk who have experienced homelessness
- Assess the acceptability of patient-reported and biometric outcome measures including point of care laboratory protocols
- Refine protocols for incentives and tools to support intervention participation and behavior change

3 INVESTIGATIONAL PLAN

3.1 General Schema of Study Design

This is a single arm pilot trial to inform development of the CV-HOMES behavioral treatment, see Table 1 above. The intervention targets cardiovascular health and psychological wellness using goal-setting support, as well as resource and care coordination for people experiencing elevated cardiovascular risk and homelessness. The goal of this treatment development phase of our work is to refine approaches and protocols for further study of our program.

3.1.1 Screening Phase and Baseline Assessment

Recruitment protocols are summarized in section 9.5. Screening will be conducted by phone or in-person as requested by participants. It will focus on ensuring they meet inclusion criteria and assessing current health behaviors to inform which behaviors might be targeted by wellness coaches. Baseline assessment will consist of informed consent, self-reported survey items, and biometric data including cholesterol, A1c, and skin carotenoid measurement via VEGGIE METER. Blood samples for cholesterol and A1c will be collected by fingerstick and measured on the DCA Vantage, Cholestech, A1c Now Professional, or CardioChek Plus Analyzer (1-3 drops of blood). If the POC machines using small amounts of blood are malfunctioning, venous blood draws (100 microliters) may be scheduled and collected for the study at the Healthcare for the Homeless or

Hennepin Healthcare labs. Participants will be informed of results in lab letter after appointment (2023.12.21 CV-Homes.LabLetter).

3.1.2 Study Intervention

This study will be offered to willing participants as an adjunctive to usual clinic-based health care. During the screening period, participants will be encouraged and supported to continue seeing their regular health care team. If they do not have one, support will be given to help the participant schedule a primary care or cardiology appointment at Hennepin County Health Care for the Homeless, Hennepin Healthcare, or another clinic/health system of their choosing.

3.1.3 Follow-up

Participants who have completed their planned coaching sessions or requested to end their coaching sessions early will be contacted for a follow-up assessment. Participants will be informed of results in lab letter after appointment (2023.12.21 CV-Homes.LabLetter). Since the emphasis of this treatment development study is feasibility and acceptability, those ending early will be given particular attention during their post-treatment interview so that their insights and experiences can shape future adaptations to the intervention and study design.

3.2 Allocation to Groups and Blinding *Not applicable to this phase of the study.*

3.3 Study Duration, Enrollment and Number of Sites

3.3.1 Duration of Study Participation

Participants will be screened and recruited over 1-2 weeks. They will engage in 10 weekly sessions over 12-weeks with our interventionist (“wellness coach”), and they will have a 4-week period within which to complete any missed visits and their final assessment visit. This is a maximum of 16 weeks duration per participant.

3.3.2 Total Number of Study Sites/Total Number of Participants Projected

Enrollment for the study will continue until 8 participants have been recruited or when enough data has been gathered to inform future steps of treatment development.

HHRI will serve as the only site for this study. Catholic Charities offers space in the community for study related activities to minimize burden on participants. The study team will connect with other housing and community partners to identify community spaces if necessary.

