6 STATISTICAL CONSIDERATIONS

6.1 Primary Endpoint

Primary outcomes The primary endpoint of this study is the feasibility and acceptability of the program to participants in this treatment development phase. We will assess this by measuring our ability to recruit and retain participants, the dose of treatment we can deliver (i.e., participant's attendance and follow-up with scheduled sessions and treatment activities), and participants' report of their satisfaction and overall experience during participation in a structured survey (CSQ-8) and qualitative post-treatment interview. Secondary outcomes will include measures we plan to use in a future randomized pilot study (see Assessment Table).

Clinical Outcomes will occur at baseline and post-treatment. Our primary target is a composite measure of cardiovascular health developed by the American Heart Association, Life's Essential 8 (see Table 2).¹⁸ All biometric data and self-reported items will be collected and stored in REDCap.

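### Does letting enrolment close below 8 on a judgement of sufficient data undermine the recruitment outcome?

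*Combined protocol and SAP*

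**What the plan says.** The Protocol Synopsis gives a fixed size: "Total Number of Participants: 8". Section 3.3.2 is looser: enrolment continues "until 8 participants have been recruited or when enough data has been gathered to inform future steps of treatment development". The supplied text gives no criterion for sufficiency, no minimum number, no decision-maker and no requirement to record why enrolment closed.

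Recruitment is a primary matter. Section 2.1 counts "our ability to recruit and retain participants" among the outcomes for the primary objective, and section 6.1 says of feasibility and acceptability: "We will assess this by measuring our ability to recruit and retain participants".

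Section 1.3 says how this will be done: "We will examine feasibility by tracking success of planned methods of recruitment", and then "We will track the ratio of invitations to screenings and screenings to enrollments". It attaches no target value to either ratio. Section 6.3 justifies the sample size in words only, as suited to treatment development and protocol refinement.

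**The concern.** The study measures its ability to recruit, yet the team may end recruitment on its own open judgement. A team that struggled and stopped at 4, and a team that learned enough from 4 and stopped, would both report 4 enrolled. The results are meant to inform a later randomized pilot, and the two readings call for different recruitment plans there. If the count were the recruitment outcome, the clause would let the investigators choose the value of part of their own primary endpoint, and a shortfall could be presented as sufficiency.

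**Working it through.** **1. The plan's own figure.** The size of 8 comes with no alpha, power, rate, precision or dropout input (section 6.3). There is no calculation to reproduce and none that a smaller number would invalidate.

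**2. What a smaller number does to the named measures.** The documents give no screening counts, so the counts here are assumed. The ratio of enrolled to screened is 4/5 = 0.80 in a study that stops at 4 and 8/10 = 0.80 in one that reaches 8. The estimate is the same; only its precision differs. The exact (Clopper-Pearson) 95% limits for x of n are the 0.025 quantile of Beta(x, n − x + 1) and the 0.975 quantile of Beta(x + 1, n − x). When x = n the lower limit is 0.025^(1/n) and the upper limit is 1.

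| Assumed result | Exact 95% interval | Width (points) |
|---|---|---|
| Enrolled/screened 4/5 | 28.4% to 99.5% | 71.1 |
| Enrolled/screened 8/10 | 44.4% to 97.5% | 53.1 |
| Retained 4/4 | 39.8% to 100% | 60.2 |
| Retained 5/5 | 47.8% to 100% | 52.2 |
| Retained 8/8 | 63.1% to 100% | 36.9 |

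Even the full 8, all retained, leaves retention as low as 63.1% within the interval. The loss from stopping early is one of degree.

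**3. What a smaller number does to learning.** The chance of meeting at least one participant with a problem of assumed prevalence 20% is 1 − 0.8^n: 83.2% at n = 8, 67.2% at n = 5 and 59.0% at n = 4. This is the real price of stopping early. The team would pay it knowingly, having judged that it had learned enough.

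**4. What the ratios do not show.** They carry no time. With assumed weeks, 4 enrolled in 8 weeks is 4/8 = 0.50 per week, the pace that gives 8 in 16 weeks (8/16 = 0.50). Four enrolled in 16 weeks is 4/16 = 0.25 per week, half that pace. Both can share the same ratios, and enrolment dates separate them. Signed consent is taken at the baseline visit (sections 4.1.2 and 9.6), tracking forms link each enrolled participant to a consent form (section 9.2), and section 9.3 describes a limited dataset that may include dates. Pace can therefore probably be derived, although no section promises to report it.

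**5. How open-ended the clause is in practice.** The protocol is dated 03/19/2024, and section 9.2 puts the end of the study at 10/31/2024, which is 226 days later. Section 3.3.1 says of participation: "This is a maximum of 16 weeks duration per participant", or 112 days. A participant who uses all of it must enrol by about 11 July 2024. If enrolment began near the protocol date (assumed, since no start date is given), the window is 226 − 112 = 114 days, about 16 weeks. The calendar already bounds enrolment.

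**6. What depends on reaching 8.** The supplied text states no recruitment rate, progression criterion or analysis that requires 8. Section 6.2.2 is descriptive throughout. Enrolling all 8 would not define success, and enrolling 5 would not define failure.

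**The case for a change.** The strongest case for a change is that the remedy costs almost nothing: replace the clause with 8 or a stated closing date, whichever comes first, and report the weeks taken and the reason for closing. The calendar gives this some force, because a close driven by the approaching end of the study could be described afterwards as having enough data. The ratios would not expose that, and no section asks for the reason to be recorded.

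What stands is that the count alone is ambiguous, and that the report should give the dates enrolment opened and closed and the reason. An analyst writing up recruitment would include these as a matter of course, using records the study appears to hold. The Assessment Table and the tracking forms are not in the supplied text, so their absence from it is weak evidence that such items go unrecorded.

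The replacement rule itself does not stand. The study exists to refine procedures (sections 2.2 and 3.1), may adjust the number and length of sessions (section 1.4) and does not give every participant every survey item (section 4.1.2). Stopping once further participants would teach little is consistent with that purpose, and a fixed rule gives up that discretion without improving any planned result. Adding confidence intervals would not resolve the ambiguity either. A proportion of participants attending would first need an attendance cut-off, which the plan does not set.

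**Conclusion.** No change to the plan is needed. The clause is loosely worded, and a count below 8 would not explain itself. But recruitment is judged by the success of the methods and by two ratios that keep their meaning at any final number, and no decision depends on the count. The cost of stopping at 4 instead of 8 is wider description: in the assumed example, an interval 71.1 points wide instead of 53.1, neither of which would support more than a descriptive statement. The flexibility is a fair trade-off in a treatment-development study, and the missing detail is of a kind that analysts supply when they report.

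This conclusion rests on three assumptions: that the section 1.3 ratios are tracked as stated, that consent dates are kept so that pace can be derived, and that 8 is not used afterwards as a success threshold. If a later document made reaching 8 a condition for proceeding to the randomized pilot, the stopping judgement would need a stated basis.
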